Duration of Trial	
Duration of recruitment – The trial will be recruiting over 4½ years.
 
Duration of intervention The trial treatment will be started within 24 hours (and no more than 72 hours) after the platelet count falls to $\leq 30 \times 10^9/L$, or if the participant was admitted with a platelet count already below $30 \times 10^9/L$, starting from the first day of chemotherapy or conditioning for a stem cell transplant, and continued until the platelet count is $> 30 \times 10^9/L$ for 3 consecutive days without platelet transfusion support, or until the participant has received 30 days of treatment.
 
The main data collection for efficacy endpoints will continue for 30 days from commencement of trial treatment.
 
Duration of follow-up for each participant Adverse event data will be collected for 60 days after the first dose of trial treatment is administered, and long-term safety data regarding thromboembolic events will be collected by telephone call 120 days after the first dose of trial treatment is administered.
 
The telephone call or participant visit 4 months (120 days) after the start of the trial will define the end of the trial.
 
Duration of trial The planned trial duration is 5 years from initiation of first site to completion of analysis.

Countries of recruitment	UK Australia
Target Sample Size	616 participants at UK and Australian trial sites 308 subjects will be enrolled to receive TXA and 308 to receive the placebo
Date of first enrolment	June 2015
Recruitment Status	Recruiting: participants are being recruited
Ancillary Studies/sub-studies	At selected centres, additional blood samples will be collected from recruited participants and stored, for later central analysis, to explore the pathways of fibrinolysis and the mechanisms of action of tranexamic acid.
Contact Details for Public Queries	[contact]
Contact Details for Scientific Queries	[name]; [contact]
CTU Project Manager	[name]

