9.4. Sponsor's Responsibilities

- The CTU (Sponsor) will forward all adverse reactions, SAEs and major safety outcome reports received to the Chief Investigator (or a medically qualified delegate) for review.
- As thromboembolism and mortality are the main safety outcomes of interest, these will be reported to the DMC as they occur, within a time frame to be determined by the DMC. The DMC may wish to view unblinded or partially unblinded data.
- The CTU will review all SAE reports and forward to the DMC for review, as often as instructed by them, and also provide them as listings for review at DMC meetings. These will be copied to the Chief Investigator for review.
- Agree the planned content of both blinded and unblinded DMC reports with DMC members prior to the inclusion of the first trial participant.
- The CTU is undertaking the duties of trial sponsor and is responsible for the reporting of any SUSARs to the MHRA or its equivalent and to the research ethics committee (REC) in all countries participating in the trial, and for preparing annual safety reports to the MHRA and the REC. The reporting time-frames for SUSARs will be according to the current national regulations for the participating countries. In the UK this will be in accordance with European Directive 2001/20/EC.

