11.3.3. Safety outcomes

This trial is not powered to definitively establish the safety of the treatment with respect to the frequency of VTE. However, with the planned enrolment of 616 patients, an observed difference in frequency of VTE of 3.6% on the placebo arm and 5% or less on the TXA arm would result in a 95% confidence interval that excluded a relative risk of 3.5.

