### 1.4 Randomisation and Blinding Procedures

Participants will be randomised to antifibrinolytic therapy or placebo in a 1:1 fashion, stratified by site. Randomisation will further be balanced within blocks of varying, undisclosed sizes. Randomisation lists will be created using computer-generated random numbers.

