#### 1.5.2 Primary efficacy outcomes

616 participants will be accrued to the UK/Australian clinical trial.

The participants will be randomised in a double blind fashion to receive TXA or a matching placebo.

The clinical trial will be conducted with the primary endpoint of decreased proportion of death or WHO Grade 2 or higher bleeding among all participants receiving TXA versus placebo over 30 days. The type 1 error will be controlled at a two-sided level of 0.05. The primary endpoint will be analysed using the Kaplan-Meier (KM) method to estimate the probability of bleeding or death within 30 days in the analysis populations. Power and sample size calculations are based on a log-rank test for comparing two survival curves, as described in Collett.

It is anticipated that the UK and Australia will be able to recruit 616 participants for this trial. Under the assumption that anti-fibrinolysis results in a decrease of death or WHO Grade 2 bleeding from 43% to 32%, the 616 participants will provide 80% power to detect an observed absolute decrease in bleeding rates of 11% (a relative reduction of 26% with a NNT of 8.9) and will be judged statistically significant at the two-sided 0.05 level. The planned trial size of 616 subjects includes an additional 5% of participants above the required sample size of 586. This 5% figure is more than the proportion of participants within TOPPS (4%) that dropped their platelet count below  $50 \times 10^9/L$  but did not drop their platelet below  $30 \times 10^9/L$ . This therefore accounts for the number of participants within the trial who are randomised but never receive the trial treatment.

We do not expect there to be a problem with the assessment of the primary outcome of bleeding over the 30 day trial period, starting from the first day of administration of the study intervention. In the recent TOPPS trial, completeness of bleeding outcome documentation was

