### 1.5.3 Safety outcomes

This trial is not powered to definitively establish the safety of the treatment with respect to the frequency of venous thromboembolism (VTE). However, with the planned enrolment of 616 participants, an observed difference in frequency of VTE of 3.6% on the placebo arm and 5% or less on the TXA arm would result in a 95% confidence interval that excluded a relative risk of 3.5.

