### Safety outcomes

- Number of thrombotic events from first administration of trial treatment up to and including 120 days after the first dose of trial treatment is received, per day at risk, will be described by arm.
- Number of participants developing Veno-occlusive Disease (VOD; Sinusoidal obstructive syndrome, SOS) within 60 days of first administration of trial treatment, will be described by arm.
- All-cause mortality during the first 30 days and 120 days after the first dose of trial treatment is administered will be estimated by the Kaplan-Meier method and compared using Cox regression analysis. Participants withdrawn or lost to follow up before day 30/day 120 will be censored at the time that they withdrew/were lost to follow up.
- Death due to thrombosis during the first 120 days after the first dose of trial treatment is administered will be estimated using the cumulative incidence function, with the competing risk of death due to other causes. To accommodate a random centre effect, Cox regression analysis will be used to compare death due to thrombosis between treatment arms. Participants who have not died will be censored at day 120 or at the point of last contact, whichever is first. Participants who died prior to day 120 from other causes will be censored at the time of death. If numbers of deaths due to thrombosis are very small, the number of deaths will simply be described by arm.
- Death due to bleeding during the first 30 days after the first administration of trial treatment is received will be estimated using the cumulative incidence function, with the competing risk of death due to other causes. To accommodate a random centre effect, Cox regression analysis will be used to compare death due to bleeding between treatment arms. Participants who have not died will be censored at day 120 or at the point of last contact, whichever is first. Participants who died prior to day 120 from other causes will be censored at the time of death. If numbers of deaths due to bleeding are very small, the number of deaths will simply be described by arm.
- Number of serious adverse events from first administration of trial treatment until 60 days after the first dose of trial treatment is administered, per day at risk, will be summarised by arm, including number of symptomatic thrombotic events (venous thromboembolisms and arterial ischaemic events), veno-occlusive disease, sepsis, organ failure and deaths.

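### The design section states what the trial can show about thrombosis as a 95% confidence interval for a relative risk, but the analysis plan only describes thrombotic events by arm and specifies no ratio or interval

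*SAP*

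**What the plan says.** **Design.** SAP 1.5.3 first says that the trial is not powered to settle VTE safety. It then supposes observed VTE of 3.6% with placebo and at most 5% with TXA among 616 enrolled, and says that this "would result in a 95% confidence interval that excluded a relative risk of 3.5". Protocol 11.3.3 gives the same figures: a "95% confidence interval that excluded a relative risk of 3.5". The total comes from SAP 1.5.2 ("616 participants will be accrued to the UK/Australian clinical trial") and the arm sizes from the Protocol synopsis ("308 subjects will be enrolled to receive TXA and 308 to receive the placebo").

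**Status of the outcome.** Protocol 9.4 begins a reporting rule with "As thromboembolism and mortality are the main safety outcomes of interest". Protocol 11.4 and SAP 4.1 say that randomisation is not meant to stop if the treatment looks effective at the interim. The reason given is that more safety information is needed and power for thromboembolic events is low.

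**Analysis.** SAP 4.4 says thrombotic events, "per day at risk, will be described by arm". Protocol 11.5.1 says the same. In SAP 5.5 the safety outcomes table shows this row as N, with no ratio row beneath it, and the safety data summary gives venous and arterial events as numbers only. SAP 4.2 requires a 95% CI with every ratio, but no ratio is specified for thrombotic events or VTE, so that rule supplies nothing here.

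**The concern.** The quantity used to describe the trial's information on VTE is not among the quantities it plans to report. The measures differ too. The design statement concerns the frequency of VTE, compared as a relative risk. The analysis concerns all thrombotic events, counted per day at risk. The tables count participants with at least one serious adverse event, but not participants with at least one VTE.

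Other outcomes are treated more fully. All-cause mortality gets a hazard ratio with a CI. So does death due to thrombosis, unless such deaths are very few, although it must be rarer than thrombosis itself. Days with fever get an odds ratio with a CI.

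What is at stake is the safety conclusion. Protocol 11.3.1 makes a change in practice conditional on no new safety issue emerging. Two similar counts without an interval are easily read as no difference, when the data may be compatible with a substantial increase.

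**Working it through.** **Inputs.** 308 per arm (Protocol synopsis), consistent with 616 allocated 1:1 (SAP 1.4 and 1.5.2). Observed VTE is 5% on TXA and 3.6% on placebo (SAP 1.5.3). Expected participants with VTE: 0.05 × 308 = 15.4 and 0.036 × 308 = 11.09.

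**The plan's own statement.** The documents name no interval method, so I start with the usual log-scale (Katz) interval:

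- RR = 0.05 / 0.036 = 1.39
- SE(log RR) = √(0.95/15.4 + 0.964/11.09) = √(0.0617 + 0.0869) = 0.386
- 95% CI = 1.39 × exp(±1.96 × 0.386) = 0.65 to 2.96

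The upper limit is below 3.5, so the statement is reproduced as worded.

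**Sensitivity to method and to the number treated.** SAP 4.2.3 restricts the thrombosis analysis to participants who receive any trial treatment, so the denominator may be below 616. As an illustration I use 586 (293 per arm), the required size before the 5% allowance in SAP 1.5.2.

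| Method | Data | Upper 95% limit |
|---|---|---|
| Katz RR | 308 per arm, 5% v 3.6% | 2.96 |
| Score (Koopman) RR | 308 per arm, 5% v 3.6% | 2.91 |
| Katz RR | 308 per arm, 15 v 11 participants | 2.92 |
| Katz RR | 293 per arm, 5% v 3.6% | 3.01 |
| Poisson rate ratio, equal follow-up | 308 per arm, 15.4 v 11.09 events | 3.01 |
| Exact conditional rate ratio, equal follow-up | 15 v 11 events | 3.28 |

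For the Poisson row, SE = √(1/15.4 + 1/11.09) = 0.394, and 1.39 × exp(1.96 × 0.394) = 3.01. Every limit in the table is below 3.5. Not every one is below 3.0.

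**What the planned output would show.** In this scenario the tables would give about 15 v 11 events with time at risk. They would not give the ratio of 1.39 or the range from about 0.65 to about 3.0 that tells a reader how little has been excluded.

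**The case against.** **Description is a deliberate choice.** The Protocol and SAP agree on it, both disclaim power for VTE, and veno-occlusive disease is handled the same way. This stands as an argument against a hypothesis test. It does not argue against an interval, which is the honest way to report a sparse comparison, and the design sections themselves turn to an interval straight after the disclaimer. With some 26 participants with VTE in the planned scenario, an interval can be calculated.

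**A reader can work it out.** SAP Appendix 1 lists thrombotic events by participant, arm and event type, and venous and arterial events are tabulated separately. Participants with VTE could therefore be counted by hand and a relative risk derived. That is true, so no information is lost. But a figure a reader may construct is not a pre-specified estimate with a stated method and population.

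**Oversight during the trial.** The data monitoring committee receives thromboembolism reports as they occur and an interim summary by arm. The point therefore concerns the final report, not participant protection during the trial.

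**Stronger readings that the documents do not support.** A reader might infer that 3.5 is a miscalculation because the usual interval stops near 3.0. The documents say that 3.5 is excluded, not that it is the limit, and the working shows this to be true. Replacing it with 3.0 would be less safe: 3.0 is not excluded at 293 per arm, nor by the Poisson or exact rate ratio. A reader might also infer that the trial was sized on VTE. It was not: 616 comes from the primary outcome, and the VTE sentence only illustrates precision.

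**Conclusion.** The gap is real but limited: neither the analysis section nor the table shells specify a relative risk, rate ratio or confidence interval for thrombotic events or VTE, although the design section uses such an interval to say what the trial can show. In the plan's own scenario the missing result is RR 1.39, 95% CI 0.65 to 2.96, with an upper limit between about 2.9 and 3.3 depending on method and number treated. These figures assume the observed rates in SAP 1.5.3 and, for the rate ratios, equal follow-up in the two arms. The gap itself depends on none of them. The sentence about 3.5 is correct as it stands. The point deserves correction because thromboembolism is a main safety outcome and safety information is the stated reason for carrying on past an efficacy signal.

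**What to change.** In SAP 4.4 and the safety outcomes table in SAP 5.5, add for the treated population:

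- the number of participants with at least one VTE in each arm, and the relative risk, TXA v placebo, with a 95% CI;
- the rate ratio of thrombotic events per day at risk, TXA v placebo, with a 95% CI.

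Name the interval method in advance, with an exact or score interval if events are sparse, and leave the P value column empty for these rows. SAP 4.2 asks for a random site effect in every model, so say whether these intervals are unadjusted. The participant-level relative risk also covers the case where one person has several events, which a simple rate ratio would treat as independent. Repeat the wording in Protocol 11.5.1 if the Protocol is next amended. Protocol 11.3.3 and SAP 1.5.3 need no change.

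The cost is a few table rows and two sentences. No new data are needed, and the sample size and primary analysis are unaffected.

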7.2.3. Other outcomes

All measured during first 30 days of the trial, i.e. **from the first dose of trial treatment**

- Proportion of days with thrombocytopenia ($\leq 10 \times 10^9/L$, $\leq 30 \times 10^9/L$, $\leq 50 \times 10^9/L$)
- Proportion of days with fever (highest daily temperature $\geq 38.1^\circ\text{C}$) of days spent in hospital, up to study day 30
- Reasons for platelet and red cell transfusions

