- Proportion of days with thrombocytopenia ($<10 \times 10^9/L$, $<30 \times 10^9/L$, $<50 \times 10^9/L$) will be analysed using logistic regression.
- Proportion of days with fever (highest daily temperature $\geq 38.1^\circ C$) of days spent in hospital, up to study day 30, will be analysed using logistic regression.
- Reasons for platelet and red cell transfusions; the reasons will be described by arm.

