## Statistical Analysis Plan

---

excellent. A bleeding assessment was completed on 93% (8405/9030) of days for participants in the no-prophylaxis group, and 97% (8733/8970) of days in the prophylaxis group. The majority of participants in both arms had bleeding information completed on each trial day (median no-prophylaxis 30 days (IQR 29 to 30); median prophylaxis 30 days (IQR 30 to 30)). There were also only 6 deaths (1% of participants) while on the trial.

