#### 2.2.2 Secondary Safety Outcomes

- Number of thrombotic events from first administration of trial treatment up to and including 120 days after the first dose of trial treatment is administered, per day at risk
- Number of participants developing Veno-occlusive Disease (VOD; Sinusoidal obstructive syndrome, SOS) within 60 days of first administration of trial treatment
- All-cause mortality during the first 30 days and the first 120 days after the first dose of trial treatment is administered
- Death due to thrombosis during the first 120 days after the first dose of trial treatment is administered
- Death due to bleeding during the first 30 days after the first dose of trial treatment is administered

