### 2.2.3 Other Outcomes

All measured during first 30 days of the trial, i.e. **from the first day of administration of the study intervention.**

- Proportion of days with thrombocytopenia ( $\leq 10 \times 10^9/L$ ,  $\leq 30 \times 10^9/L$ ,  $\leq 50 \times 10^9/L$ )
- Proportion of days with fever (highest daily temperature  $\geq 38.1^{\circ}C$ ) of days spent in hospital, up to study day 30
- Reasons for platelet and red cell transfusions

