### 4.4 Analysis of secondary outcome measures

#### **Secondary efficacy outcomes**

- Proportion of days with bleeding up to study day 30 will be compared by treatment arm using binary logistic regression analysis (bleeding or not on any given day). Correlation at participant level will be accounted for by including a random participant effect.
- Time to first episode of bleeding of WHO grade 2 or greater up to study day 30 will be estimated using the cumulative incidence function, with the competing risk of death prior to bleeding of WHO grade 2 or greater. Median, IQR will be reported by treatment arm. To accommodate a random centre effect, Cox regression analysis will be used to compare time to first episode of bleeding of WHO grade 2 or greater between treatment arms. Participants who have not experienced bleeding of WHO grade 2 or greater will be censored at day 30 or at the point of last contact, whichever is first. Participants who died prior to study day 30 and did not experience bleeding of WHO grade 2 or greater will be censored at the time of death. The estimate of the hazard of bleeding of WHO grade 2 or greater from this model should be interpreted with caution because it does not properly account for the competing risk of death. However, since the number of deaths are predicted to be small, the impact of the competing risk is likely to be negligible. This will be explored by examining the cumulative incidence function for death prior to bleeding of WHO grade 2 or greater.
- Highest grade of bleeding up to study day 30 will be compared by treatment arm using an ordinal logistic regression model, modelling grade as an ordinal categorical outcome.
- Number of platelet transfusions/participant up to study day 30 will be compared by treatment arm using a negative binomial model. The model will include an offset to account for the number of days the participant spent in hospital, up to 30 days or to the last point of contact, whichever is first. In addition, unadjusted median, IQR number of platelet transfusions per day in hospital will be reported.
- Number of red cell transfusions/participant up to study day 30 will be compared by treatment arm using a negative binomial model. The model will include an offset to account for the number of days the participant spent in hospital, up to 30 days. In addition,

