**Table xx      Safety outcomes table**

Outcome	Active arm (n=)	Placebo arm (n=)	Overall (n=)	P value
All-cause mortality during the first 30 days after the first dose of trial treatment is administered – % (95% CI)				
Hazard ratio (95% CI)				
All-cause mortality during the first 120 days after the first dose of trial treatment is administered – % (95% CI)				
Hazard ratio (95% CI)				
Number of thrombotic events from first administration of trial treatment up to and including 120 days after the first dose of trial treatment is received, per day at risk (N)				
Number of participants developing Veno-occlusive Disease within 60 days of first administration of trial treatment (N)				
Death due to thrombosis during the first 120 days after the first dose of trial treatment is administered – % (95% CI)				
Hazard ratio (95% CI)				
Death due to bleeding during the first 30 days after the first administration of trial treatment is received – % (95% CI)				
Hazard ratio (95% CI)				

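### Death due to bleeding within 30 days is censored at day 120, and thrombocytopenia days are analysed with a start point, inequality and fallback that depart from their definition

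*SAP*

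**What the plan says.** **Death due to bleeding.** SAP 2.2.2 lists "Death due to bleeding during the first 30 days after the first dose of trial treatment is administered", and the safety outcomes table in SAP 5.5 has a row for "Death due to bleeding during the first 30 days after the first administration of trial treatment is received". Protocol 7.2.2 and 11.5.1 give the same 30-day window; 11.5.1 names no censoring day for this outcome. The SAP 4.4 item also opens with 30 days, but its censoring rules for survivors and for other-cause deaths both name day 120. The second rule, and the small-numbers provision after it, run "day 120 from other causes will be censored at the time of death. If numbers of deaths due to bleeding are very small". The two rules are worded as in the thrombosis-death item directly above, where the window is 120 days. In time to first grade 2 bleed, the other 30-day competing-risk outcome in SAP 4.4, participants without the event "will be censored at day 30 or at the point of last contact, whichever is first".

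**Thrombocytopenia days.** Protocol 7.2.3 and SAP 2.2.3 define these as days at or below 10, 30 and 50 × 10⁹/L. Protocol 7.2.3 counts from the first dose and SAP 2.2.3 "from the first day of administration of the study intervention". Protocol 11.5.1 changes the inequality: "Proportion of days with thrombocytopenia ($<10 \times 10^9/L$, $<30 \times 10^9/L$, $<50 \times 10^9/L$) will be analysed using logistic regression". SAP 4.5 also uses strict inequalities and starts at consent. The SAP 5.7 table uses strict inequalities and starts at randomisation, including in its row for missing counts.

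**Fallback.** Each of the three thrombocytopenia items in SAP 4.5 replaces the arm comparison with a description when thrombotic events are very few. The fever item beside them uses the same model and has no such condition.

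**The concern.** A pre-specified outcome should give one result per label. Here two analysts following the text could differ.

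- **Bleeding death.** One would report a 30-day hazard ratio. The other would report a 120-day hazard ratio beside a 30-day percentage, under the same row label.
- **Thrombocytopenia days.** The count could start at consent, randomisation or day 1. Days before the first dose cannot reflect treatment, so they dilute the comparison, equally in both arms and without evident bias. A count of exactly 10, 30 or 50 is classified against the definition. These values are also the trial's own at-or-below triggers for prophylactic platelets (protocol 6.4.1), starting treatment (6.2.4) and randomisation (5.5).
- **Fallback.** A planned comparison can be cancelled by the count of an unrelated outcome.

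**Working it through.** The documents give no figure to reproduce for these outcomes. The check compares the passages and then sizes the consequences on stated assumptions.

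**1. Start points, cut-offs and windows side by side**

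| Outcome | Definition | Analysis text | Results table |
|---|---|---|---|
| Death due to bleeding | 30 days (protocol 7.2.2, SAP 2.2.2) | 30 days, censored at day 120 (SAP 4.4) | 30 days (SAP 5.5) |
| Thrombocytopenia days, start | first treatment (protocol 7.2.3, SAP 2.2.3) | consent (SAP 4.5) | randomisation (SAP 5.7) |
| Thrombocytopenia days, cut-off | ≤10, ≤30, ≤50 | <10, <30, <50 (SAP 4.5, protocol 11.5.1) | <10, <30, <50 (SAP 5.7) |

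**2. Bleeding death: effect of the censoring day**

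*Only deaths to day 30 counted as events.* Moving the censoring day adds no events. In one simulated data set with 308 per arm and 18 events to day 30, the Cox hazard ratio was 0.496 with censoring at day 30 and 0.496 with censoring at day 120. The cumulative incidence read at day 30 is also unchanged.

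*Later deaths also counted.* Assume a hazard ratio of 0.5 to day 30 and 1.0 afterwards, and let s be the share of placebo bleeding deaths that fall by day 30. For rare events, HR to day 120 ≈ s × 0.5 + (1 − s) × 1.0:

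- s = 0.75: 0.375 + 0.25 = 0.625 (simulation 0.636)
- s = 0.50: 0.25 + 0.50 = 0.75 (simulation 0.749)
- s = 0.25: 0.125 + 0.75 = 0.875 (simulation 0.865)

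A separate calculation used 293 per arm and assumed placebo risks of 1–2% to day 30 and 1–3% on days 31–120. It gave 0.66 to 0.87.

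*Likely event numbers.* SAP 1.5.2 says of TOPPS: "There were also only 6 deaths (1% of participants) while on the trial". Applied here, 1% × 616 ≈ 6 deaths from all causes, so bleeding deaths over a similar period would be fewer still.

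**3. Thrombocytopenia days: effect of the start point**

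The interval from consent to day 1 is not given. Let k be the number of pre-treatment days, the same in both arms and with the same proportion of thrombocytopenic days in both. The pre-treatment share is k/(k + 30), and a true difference in proportions keeps 30/(30 + k) of its size:

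| k (assumed) | Pre-treatment share | Difference retained |
|---|---|---|
| 3 | 3/33 = 9% | 30/33 = 0.91 |
| 7 | 7/37 = 19% | 30/37 = 0.81 |
| 14 | 14/44 = 32% | 30/44 = 0.68 |

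A randomisation start obeys the same formula, with k counted from randomisation.

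The SAP reports an odds ratio. Assume 40% against 35% of days over 30 treatment-period days and 10% in both arms before treatment. The odds ratio with no pre-treatment days is (0.35/0.65)/(0.40/0.60) = 0.81. Adding 5 to 14 such days moves it to 0.83–0.85 and shrinks the difference from 5.0 to 4.3–3.4 percentage points.

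How often a count falls exactly on a cut-off is not given, so that part is not sized.

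**4. Fallback**

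Eligibility anticipates a count at or below 10 for at least 5 days. As a rough guide, 586 × 5 = 2,930 person-days. A fallback worded on thrombocytopenic days would therefore not be expected to trigger.

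**The case against.** **Bleeding death.** Every definition limits the event to 30 days, and only the censoring sentences say otherwise. An analyst who follows the definition gets the same hazard ratio either way. The 0.63–0.88 range rests on an assumed effect and assumed timing, and the Cox check used 18 deaths by day 30, three times the plan's all-cause benchmark. At that benchmark the item may end as a description. All of this stands. It does not settle which window the item means: the protocol gives no censoring day, the threshold for very small numbers is undefined, and the count it tests itself depends on whether deaths are taken to day 30 or day 120. The six deaths were also recorded during that earlier trial, so they say little about 120 days.

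**Thrombocytopenia days.** This is an outcome in the lowest tier, the trial hypothesis does not concern platelet counts, and the odds ratio moves little in the illustration. The consent start also matches the platelet-count plot in SAP 4.5, so it may be deliberate. These points limit the consequence. They do not explain why the definition, the analysis and the table each start on a different day.

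**Fallback.** The words are plausibly a slip for thrombocytopenia. The illustrative rates in SAP 1.5.3 give about 308 × 3.6% = 11 and 308 × 5% = 15 venous events, so the literal condition may never be met. The 2,930 days are only approximate: eligibility is an expectation stated with ≤10, the analysis uses <10, and platelets are transfused at ≤10. The sentence still makes a planned comparison depend on the wrong outcome.

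**Conclusion.** The concern holds on all three parts. They are analysis rules that contradict the plan's own definitions, and they should be corrected, although the primary analysis is untouched.

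The consequence is modest and conditional. For bleeding death it ranges from no change to a hazard ratio moved from 0.5 to roughly 0.63–0.88, and the latter requires deaths after day 30 to be counted and the assumed effect pattern to apply. For thrombocytopenia days the start point costs 9% to 32% of a true difference in proportions, if consent precedes treatment by 3 to 14 days; those intervals are assumptions, and the documents do not predict any such difference. The effect of the inequality cannot be sized from the documents. The fallback matters only if thrombotic events are judged very few, a threshold that the SAP leaves undefined.

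**What to change.** - **SAP 4.4, death due to bleeding:** change both day-120 entries to day 30.
- **SAP 4.5 and the SAP 5.7 thrombocytopenia table:** use ≤10, ≤30 and ≤50 × 10⁹/L from day 1 to day 30, in the three analysis items, the three outcome rows and the missing-counts row. The platelet-count plot can keep its consent start.
- **Protocol 11.5.1:** align the strict inequalities with protocol 7.2.3.
- **SAP 4.5, fallback:** delete the thrombotic-event sentence from the three thrombocytopenia items, or tie it to the number of thrombocytopenic days. Deletion is simpler, since that condition is not expected to be met.

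The cost is a few words in two SAP sections, one SAP table and one protocol line. No new data are needed.
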